For the integrated intervention, or “intervention package”⁸⁶ that combines screening and depression care management, we will adapt the evidence-based Three Component Model (TCM) of collaborative care,^{97,98,57} and we will incorporate additional evidence-based socio-cultural collaborative care elements developed by Ell and colleagues.^{95,99} TCM, funded as part of the MacArthur Foundation Initiative on Depression and Primary care, provides a system for depression management as recommended by the U.S. Preventive Services Task Force, and its structure is complementary to that of PCM. Components include telephone care management, collaboration between mental health and primary care professionals, and preparation of primary care clinicians and practices to provide systematic depression management through training. Based on Ell’s successful collaborative care trials with low-income Hispanic populations^{95,99} we will draw on her work to add the following elements to TCM: 1) psychoeducation to dispel treatment misconceptions, reduce stigma associated with depression, and enhance the therapeutic alliance; and 2) patient navigation assistance specifically to facilitate patient self-efficacy, patient-provider communication, access to financial and social resources, with a focus on specific behavioral activities to complete screening examinations and follow-up (e.g., scheduling appointments, reminders, transportation).

Outcomes include: reduced depression, improved quality of life, improved satisfaction with healthcare decisions, increased self-efficacy, decreased internalized stigma, and decreased likelihood of morbidity and mortality from breast, cervical, and colorectal cancer.

Main Hypotheses

Our hypothesis that the 12-month CCI intervention we will implement at the six participating sites will be significantly more effective than the PCM comparison condition in improving key patient-reported outcomes associated with cancer screening and depression, including cancer screening knowledge and attitudes, self-efficacy, depression-related stigma, provider referrals, participation in mental health care, medication adherence, quality of life, and satisfaction with care and treatment decisions, and depression (**Aim 1**).

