We expect the intervention to have a positive impact on screening participation itself (**Aim 2**) by reducing depression (**Aim 3**) and by influencing patient-reported outcomes associated with screening. Finally, as shown, we hypothesize that the effectiveness of CCI in comparison to the PCM condition in increasing screening may vary depending on patient characteristics, such as duration of depression, presence of other chronic conditions, obesity, personal experience with cancer, and demographic characteristics (**Aim 4**); we also hypothesize that depression outcomes will vary according to these patient characteristics as well. We recognize that change has both intended and unintended consequences and is not linear. However, our model depicts the hypothesized pathways for the study and analysis as described; any additional analyses of bi-directionality will be exploratory.

To determine the effectiveness of the CCI intervention in increasing cancer screening over a one-year period, we will compare it to the performance of the traditional PCM cancer screening intervention among depressed women who are non-adherent with one or more screenings. Because PCM has demonstrated effectiveness among health center patients of the Bronx in general, such a comparison will be an ideal test of whether addressing and reducing depression are necessary steps to increase rates of screening among low-income depressed women. Utilizing a “usual or standard care” group as the comparison condition instead of the PCM intervention would make it impossible to isolate the effect of adding the depression reduction collaborative care components to PCM. Moreover, because PCM has already been demonstrated to be effective our MHC Connection partnership felt that offering PCM as the comparison condition would be the most ethical approach. If we find that PCM alone works just as well among depressed women as our new, integrated CCI intervention – i.e., if our findings do not enable us to reject the null hypothesis – this too has important implications for the delivery of patient-centered screening interventions in the Bronx and in other areas with a high density of low-income minority populations.

Intervention Content

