We will recruit 800 women to the study. To be eligible for the study, women must be patients at one of the six participating Bronx CHCs. They must also be between 50 and 64 years of age, speak English or Spanish, reside in the Bronx, screen positive for depression based on the PHQ-9 (≥ 8) at time of recruitment, and be out-of-adherence with current U.S. Preventive Services Task Force cancer screening guidelines for breast, cervical, and/or colorectal cancer screening. Women will be considered out of adherence if they have not received a Pap test without HPV in the past three years or a Pap test with HPV in the past five years, a mammogram in the past two years, and/or one of the following forms of colorectal screening: FOBT (or FIT) within the past year, flexible sigmoidoscopy in the past five years, or colonoscopy in the past 10 years. A woman who has had total hysterectomy is considered up-to-date for cervical cancer screening after the date on which the hysterectomy was performed.⁷⁶ We aim to be as inclusive as possible in this study. However, to maximize feasibility and in keeping with prior collaborative care research^{99,112}, we will exclude women who report the following when screened: terminal illness, current pregnancy (albeit unlikely in this age range), substance use, decisionally impaired or suicidal thoughts. We will exclude prisoners. Data received from the six health center sites support the availability of potential study participants and demonstrate the need for a study such as this one. In 2011, across the study sites, mammography rates for women 50-64 years of age were 56%, 57% and 64%; Pap testing rates were 62%, 50% and 53%. All of these rates fell substantially below the New York City target of 85% or greater. For colon cancer screening, rates in 2011 were 24%, 52%, and 27%, also much lower than the New York City target of 60% or greater. Additionally, depression rates for women of this age range in 2011 were 35% (including dysthymia), 21%, and 21%, which is consistent with the literature.

H. RECRUITMENT OF SUBJECTS

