Colonoscopy) were compared separately between the two intervention arms using a chi square test comparing two independent binomial proportions (Aim 1). Next, logistic regression was used to control for potential confounders, including the factors discussed that were identified as being unevenly distributed between the CCI and PCM intervention arms at baseline. To account for possible differences by site, site indicators were included in the model as a fixed effect to examine if there were potential confounders; if they were not found to be confounders, they were removed from the model. A combined ordinal cancer screening outcome, calculated as number of up to date cancer screening tests (which vary from 0 to 3) was analyzed using the proportional odds model (PROC GENMOD in SAS). Other key patient-reported outcomes, including changes in depression, self-efficacy, stigma, satisfaction with cancer screening decision and satisfaction with care, and quality of life, were also compared between the two intervention arms (Aim 2). For continuous outcomes, a two-sample t-test was used to examine the difference between the two arms, and a linear regression model was used to control for potential confounders; for categorical outcomes, a chi-square test was used to examine the difference between the two arms and a logistic regression (for binary outcome) or a multinomial logistic regression (for a categorical outcome with more than two levels) was also used to control for potential confounders.

Multivariate analyses testing for moderators and mediators

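### The Protocol treats failure to reject the null as showing that PCM works as well as CCI, but the trial is built only to detect a difference

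*Protocol*

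**What the plan says.** The Main Hypotheses subsection of Protocol Section B sets out superiority hypotheses. On patient-reported outcomes, CCI "will be significantly more effective than the PCM comparison condition". On screening, "We expect the intervention to have a positive impact on screening participation itself".

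The same subsection then justifies PCM, rather than usual care, as the comparator. It says that "such a comparison will be an ideal test of whether addressing and reducing depression are necessary steps to increase rates of screening" and closes by considering a null result: "If we find that PCM alone works just as well among depressed women as our new, integrated CCI intervention", which it explains, after an i.e., as "if our findings do not enable us to reject the null hypothesis". It says that such a result would have important implications for delivering screening interventions in the Bronx and in similar areas.

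In the SAP (Intention to treat analysis), the three screening outcomes "were compared separately between the two intervention arms using a chi square test comparing two independent binomial proportions". The number of up-to-date tests, 0 to 3, goes into a proportional odds model. The Sample size/Power Calculation section claims about 80% power with 356 women per arm to detect a 10% difference at two-sided 5%, under unstated PCM rates. It calls that 10% the smallest difference of interest and attributes it to studies of PCM against usual care. The figure is used for power only.

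**The concern.** Failing to reject a hypothesis of no difference is not evidence of no difference. It can happen because the arms are alike, or because the trial was too imprecise to separate them. To conclude that PCM does as well as CCI, the data must exclude a CCI advantage large enough to matter, and that needs a margin or at least a confidence interval read against a benchmark. Neither document provides one for this conclusion.

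At stake is the message from a null trial. The Protocol says in advance that this message matters for service delivery, and the same paragraph presents the comparison as a test of whether tackling depression is a necessary step. A reader who follows the clause could conclude that depression care adds nothing to screening uptake, from data still compatible with a benefit that the SAP itself counts as of interest.

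**Working it through.** **Inputs.** From the SAP, Sample size/Power Calculation: n = 356 per arm, 1:1 allocation, two-sided 5%, a 10% difference. I read the last as 10 percentage points. The PCM rate is not given, so I assume 30–60% and show values outside that range as well. The chi-square test of two proportions is equivalent to the pooled z test used here.

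**1. Reproducing the stated power.** Power ≈ Φ[(d − 1.96·SE₀)/SE₁], where SE₀ = √(2p̄(1−p̄)/n) is pooled and SE₁ = √([p₁(1−p₁) + p₂(1−p₂)]/n).

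At 30% vs 40%: SE₀ = √(2×0.35×0.65/356) = 0.03575 and SE₁ = √((0.21+0.24)/356) = 0.03555. Then (0.10 − 0.0701)/0.03555 = 0.842, so power is 80.0%, as stated. It is also 80.0% at 60% vs 70%. The lowest value is 76.2%, at 45% vs 55%.

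**2. How often a true 10-point benefit is non-significant** (1 − power, per screening test):

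| PCM rate | 20% | 30% | 35% | 40% | 45% | 50% | 55% | 60% | 70% |
|---|---|---|---|---|---|---|---|---|---|
| Non-significant | 13.0% | 20.0% | 22.1% | 23.4% | 23.8% | 23.4% | 22.1% | 20.0% | 13.0% |

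Exact binomial enumeration over 30–60% gives 19.9–24.6%. At the nine 2011 site rates in Protocol Section G (24–64%) the range is 16–23%. Those are not PCM-arm follow-up rates and serve only as reference points. If the true benefit is 5 points, non-significance is expected in 70–73% of trials at PCM rates of 30–60%.

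**3. One non-significant result.** Suppose 50% vs 56% is observed.
- z = 0.06/√(2×0.53×0.47/356) = 0.06/0.0374 = 1.60, which is not significant.
- 95% CI: 0.06 ± 1.96×0.0373 = −1.3 to +13.3 points.

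The Protocol's clause would count this as PCM doing as well as CCI, although the interval includes 10 points.

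**4. The range of such results.** For a fixed observed PCM rate, these are the observed CCI advantages at which the upper 95% limit reaches 10 points and at which significance begins:

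| PCM rate | Upper limit reaches 10 at | Significance begins at |
|---|---|---|
| 30% | 3.17 | 6.93 |
| 40% | 2.77 | 7.29 |
| 50% | 2.66 | 7.33 |
| 60% | 2.85 | 7.07 |

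Across the whole range, any observed advantage between about 3.2 and 6.9 points is non-significant and leaves 10 points inside the interval.

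**5. When the arms are truly equal.** By exact enumeration over PCM rates of 30–60%, a result is non-significant with an upper limit of at least 10 points in 14.5–21.5% of trials.

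**The case against.** The strongest reply is that the sentence is rationale for the comparator and not an analysis rule. Nowhere does the SAP say that non-rejection will be reported as equivalence. That is true and it limits the weight of the point: this is a flaw in interpretation, not in the test. But the sentence is the only text in either document that says how a null result would be read, and the SAP contains nothing to correct it.

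A second reply is that the 20–24% is ordinary type II error, shared by any trial with about 80% power, and that with equal arms most results would exclude a 10-point advantage (step 5). Both statements are right. They show that a null result could be informative, but it is the interval that shows whether a particular one is. Non-rejection alone does not.

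Third, the praise of the comparison as a test of necessity concerns the choice of comparator, not the reading of a p-value. That is fair. It shows the importance attached to the result and is not itself the error.

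Fourth, the 10-point benchmark is imperfect. The SAP attributes it to PCM versus usual-care studies, yet two of its three cited references are, by title, about primary-care treatment of depression. This is a reason to use it only as an aid to interpretation. It does not rescue the clause.

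**Conclusion.** The concern holds. The Protocol equates non-rejection with PCM working as well as CCI, in a trial whose hypotheses, tests and power are all for a difference, and with no margin or interval attached to that conclusion. On the assumptions stated (356 per arm, 10 percentage points, PCM rate 30–60%), about one in five to one in four true 10-point benefits would be misread on each screening test. The superiority analysis, its sample size and its error rate stand. The change should be made because the Protocol itself calls the null conclusion important and the correction is cheap.

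**What to change.** **Protocol, Section B, Main Hypotheses.** Delete the i.e. clause. State that a non-significant result does not by itself show that PCM works as well as CCI.

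**SAP, Intention to treat analysis.** Report the CCI − PCM risk difference with a two-sided 95% CI for each of Pap test, mammogram and colorectal screening, and the odds ratio with its 95% CI from the ordinal 0–3 model. Describe a non-significant screening-test result as inconclusive where its CI still includes a 10-point CCI advantage. Use the 10 points to guide wording only; it changes no test decision. Note the SAP's stated source for it, and that excluding 10 points does not exclude smaller benefits. The SAP is written in the past tense, so if the benchmark is added after analysis, label it post hoc. The same wording should carry into the trial report.

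**Cost.** One wording change, three intervals from existing counts and one from a model already planned. No test, sample size or error rate changes. The drawback is that some null results must be called inconclusive: about 15–21% of trials per test if the arms are truly equal. A benchmark added now also carries less weight than one set in advance.

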F. STUDY QUESTIONNAIRES AND MEASUREMENT

We chose measures that are based on the conceptual model, have been validated and used widely with minority populations, and have been translated into Spanish; as needed, we will use a translating service with forward and back translation to translate the measures. All items taken from the National Cancer Institute's HINTS survey have been translated. We organize the measures by: primary outcomes, intermediate outcomes, and co-variables.

Primary Outcomes

Participation in colorectal, breast, and cervical cancer screening

We will assess participation in age-appropriate cancer screening behaviors in two ways:

a. Chart Review: Review of electronic medical records at each of the three CHCs.

b. Self-Report: We will ask participants about their participation (yes/no) in specific screening methods: Pap testing (past 3 years), mammography (past 2 years), and colorectal screening (FOBT/FIT, past year; flexible sigmoidoscopy, the past 5 years; and colonoscopy, past 10 years). We will use standardized items from the NCI's HINTS Survey.¹²⁷

Depression

a. Patient Health Questionnaire (PHQ)-9. The PHQ-9 is the 9-item depression module from the full PHQ, and is a well-validated Diagnostic and Statistical Manual of Mental Disorders 4th Edition (DSM-IV) criterion-based measure for screening and diagnosing depressive episode, assessing severity, and monitoring treatment response,^{128,129,130,131} either in person or over the phone.¹³² It has been shown to measure a common concept of depression across racial and ethnic groups, including African Americans and Latinos.^{128,133} Cronbach's alpha was 0.80 in both African American and Latino samples.¹²⁸ As a severity measure, the score can range from 0-27, since each of the 9 items can be scored from 0 (not at all) to 3 (nearly every day). Meta-analysis showed pooled sensitivity of 0.80 and specificity of 0.92 to a diagnosis of major depression among primary care patients in a structured psychiatric interview by a mental health professional using DSM-IV diagnostic criteria.¹³¹ As a practical screening tool, patients with a score of > 10 are considered to have clinically significant depressive symptoms.^{99,134,96,112,135,129}

b. The Hopkins Symptom Checklist (SCL-20). The SCL-20 consists of the 20 depression items on a 4-point scale from the SCL-90, and has been shown to be a valid and reliable measure of depression in diverse outpatient and community populations (Cronbach's alpha = 0.87; test-retest r=0.81).^{136,137} It has been shown to be sensitive to change in studies of collaborative care in primary care settings^{99,97,121,96,112,134,135} and among minority group patients.^{95,99,133}

We will consider clinically meaningful improvement of depressive symptoms to be a > 50% reduction in baseline SCL-20 or PHQ-9, and depression remission as an SCL-20 score <0.5 or a PHQ-9<5.

Intermediate Outcomes

Quality of Life/Health Status. We will measure quality of life with the Medical Outcomes Study (MOS) Short Form Health Survey (SF-12), which includes heterogeneous items from the SF-36 physical and mental component scales. This general measure of health status assesses the patient's perceived health status and whether health problems interfere with normal functioning. The SF-12 has with demonstrated validity and test-retest reliability in the general population and in patients with chronic health conditions, and has been tested in five languages, including Spanish.¹³⁸ It has been used extensively as a quality of life measure in collaborative care studies,⁴² including with low-income minority populations.^{95,99} It has also been used frequently in screening studies, for cancer and other conditions.¹³⁹⁻¹⁴² The SF-12 has been validated as an indicator of effects of depression on quality of life in ethnically diverse patients.¹⁴³

Mental Health Care Utilization.

We will assess mental health care utilization in two ways:

c. Chart review. We will use data from the electronic medical record to determine the number of health visits, and the kind of provider seen for mental health care (psychiatrist, psychologist, and/or clinical social worker).

d. Patient report. At baseline, we will ask respondents how many times in the past six months they have seen a provider to talk about or get medication for feeling sad, nervous, hopeless, or blue. In addition, we will ask participants about their ability to arrange to get mental health treatment, as well as whether they

have the financial resources to access mental health services. These questions will be adapted from the NCI's HINTS survey.¹²⁷

Satisfaction with decision to participate in screening and mental health care. The Satisfaction with Decision Scale is a 6-item measure that uses a five-point Likert-type scale and can be tailored to any healthcare decision; it is grounded in a conceptual model of an effective decision, i.e., one that is informed, consistent with the decision-maker's values, and behaviorally implemented.¹⁰⁷ It has excellent validity and reliability (Chronbach's alpha=0.86) in samples of women 40 and older,¹⁰⁷ among depressed patients,¹⁰⁸ and among participants of a large national cancer screening trial.¹⁴⁰

Attitude Toward Cancer Screening

We will use questions from the NCI's HINTS survey¹²⁷ to assess patients' attitudes and beliefs about colon cancer screening that might prevent them from obtaining this cancer screening. We will adapt this item to also assess patients' attitudes and beliefs about cervical cancer and breast cancer screening.

Stigma associated with depression and help-seeking. *Internalized stigma*, also referred to as self or felt stigma,¹⁵⁸ will be measured with Link's Devaluation-Discrimination Scale (DDS) (Link, 1987; Link et al., 1989 and 1991). This 12- item extensively used measure, based on modified labeling theory, uses a six-point Likert format and assesses the extent to which an individual believes that people with mental illness are devalued or discriminated against (Link et al., 2004). It has established validity and reliability in diverse and low-income urban patients.^{159,160} The average Cronbach's alpha for this scale was .83.¹⁵⁸ We will also measure *stigma-related concerns about seeking care*, based a large study of low-income Black and Latina women with depression.⁷² A care-seeking stigma variable will be created from 3 yes/no in response to the query: Would any of the following keep you from getting professional help? Participants will be categorized as having stigma -related concerns if they endorse one or more of the following: being embarrassed to talk about personal matters with others, being afraid of what others might think and family members might not approve.

Satisfaction with care. In keeping with the Institute of Medicine's report Crossing the Quality Chasm (2001) and with recommendations based on a systematic literature review (Crow et al., 2002), we will use a 34-item multidimensional scale of patient satisfaction that has demonstrated high reliability and construct validity in large outpatient samples, including Medicaid patients and Spanish-speaking patients (Safran et al., 2005; Fanjiang et al., 2007). The Ambulatory Care Experiences Survey produces 11 summary measures covering 2 broad dimensions of patients' experiences: quality of physician-patient interactions and organizational features of care. All measures range from 0 to 100 points, with higher scores indicating more favorable performance. Cronbach's alphas for the 11 measures range from .70 to .90.

Self-Efficacy. We will use the 10-item General Self-Efficacy Scale (GSE).¹⁶¹ The scale measures a general sense of perceived self-efficacy associated with coping with daily hassles and adapting to stressful life events. This unidimensional scale is available in 33 languages and has Cronbach's alphas ranging from .76 to .91 based on samples from 23 countries.¹⁶² Perceived self-efficacy is an operative construct, meaning that it is related to subsequent behavior and is relevant for clinical practice and bringing about behavior change.¹⁶¹ However, it does not tap specific behavior change, and thus it will be necessary to add items to focus on the three different types of screening and utilization of needed mental health services; the development of such items will be based on the guidelines of Schwarzer¹⁶¹ as well as the valid and reliable breast cancer screening self-efficacy measurement work of Champion^{163,164}; the cervical cancer screening self-efficacy work of Fernandez;^{157,165} and research by Maly¹⁶⁶ on efficacy in patient-physician interactions.

Physician recommendation of screening/mental health care. We will use questions from the NCI's HINTS survey¹²⁷ to assess whether patients report their primary care physician has recommended cervical, breast, and colon cancer screening. We will adapt this item to determine whether their primary care physician has recommended that the patient make an appointment with a mental health provider and/or take psychotropic medication.

Mental health treatment adherence. We will ask respondents if they have been prescribed medication for depression and about difficulties taking medication(s) regularly. Questions will adapted from Katon's Team Care Intervention.¹¹²

Co-variates

Sociodemographics. We will draw the following measures from the NCI's HINTS survey;¹²⁷ race, ethnicity, age, education, language spoken, foreign born, years in the U.S., marital status, parental status, household composition, employment status, insurance status, education, and income.

Past history of cancer. We will use questions from the NCI's HINTS survey¹²⁷ to determine whether the respondent has ever been diagnosed with cancer, and if so, what type of cancer and when. We will also ask women if they have had a hysterectomy and confirm through the electronic medical record whether this was a full hysterectomy that included removal of the cervix.

Family history of cancer. Questions about family history of cancer will come from the NCI's HINTS survey.¹²⁷

Chronic medical conditions and obesity.

Information about the respondents' chronic medical conditions as well as weight, height, and body mass index as an indicator of obesity will be drawn from the electronic medical records. **Anxiety (GAD-7).** The GAD (Generalized Anxiety Disorder)-7 is based on diagnostic criteria in the DSM-IV and measures probably anxiety disorder and severity of anxiety symptoms. Patients are asked to rate how often they have been bothered by 7 problems in the last 2 weeks on a 4-point (0-4) scale ("not at all" to "nearly every day"). At a cut point of 10, sensitivity is 89% and specificity is 82%. In multiple diverse primary care samples of over 2000 patients, the measure demonstrated excellent validity as well as high internal reliability and test-retest reliability (Cronbach's alpha=0.92 and intraclass correlation=0.83, resp.).^{167,168} Factorial analysis demonstrated that the GAD-7 measures anxiety as distinct from depression.¹⁶⁸ A Spanish-language version has also demonstrated very good specificity and sensitivity as well as excellent reliability and validity.¹⁶⁹

G. STUDY SUBJECTS

We will recruit 800 women to the study. To be eligible for the study, women must be patients at one of the six participating Bronx CHCs. They must also be between 50 and 64 years of age, speak English or Spanish, reside in the Bronx, screen positive for depression based on the PHQ-9 (≥ 8) at time of recruitment, and be out-of-adherence with current U.S. Preventive Services Task Force cancer screening guidelines for breast, cervical, and/or colorectal cancer screening. Women will be considered out of adherence if they have not received a Pap test without HPV in the past three years or a Pap test with HPV in the past five years, a mammogram in the past two years, and/or one of the following forms of colorectal screening: FOBT (or FIT) within the past year, flexible sigmoidoscopy in the past five years, or colonoscopy in the past 10 years. A woman who has had total hysterectomy is considered up-to-date for cervical cancer screening after the date on which the hysterectomy was performed.⁷⁶ We aim to be as inclusive as possible in this study. However, to maximize feasibility and in keeping with prior collaborative care research^{99,112}, we will exclude women who report the following when screened: terminal illness, current pregnancy (albeit unlikely in this age range), substance use, decisionally impaired or suicidal thoughts. We will exclude prisoners. Data received from the six health center sites support the availability of potential study participants and demonstrate the need for a study such as this one. In 2011, across the study sites, mammography rates for women 50-64 years of age were 56%, 57% and 64%; Pap testing rates were 62%, 50% and 53%. All of these rates fell substantially below the New York City target of 85% or greater. For colon cancer screening, rates in 2011 were 24%, 52%, and 27%, also much lower than the New York City target of 60% or greater. Additionally, depression rates for women of this age range in 2011 were 35% (including dysthymia), 21%, and 21%, which is consistent with the literature.

H. RECRUITMENT OF SUBJECTS

Participating sites are Morris Heights Health Center, Urban Health Plan and Montefiore Primary Care Practice. We have added Segundo Ruiz Belvis and Morrisania Diagnostic and Treatment Centers and Lincoln Primary Care Practice as three additional sites. We will recruit approximately 800 women ages 50-64 who screen positive for depression and who are non-adherent with cervical, breast, and/or colorectal cancer screening guidelines from one of the participating Bronx sites. Women in this age range should receive all three types of cancer screening. We are focusing solely on women because estimates of depression among minority women in the Bronx are 20%-25%, at least twice that of men, and depression has been shown to be a barrier to screening, with consequences for cancer morbidity and mortality. Patients will be approached and screened in the participating sites in person or by phone to

determine whether they meet initial study inclusion criteria; they will have been identified as potentially eligible by the electronic medical record. Only patients who speak English or Spanish are eligible. For this screening, patients will provide verbal consent; the data will be anonymized. Patients will receive \$5 for their participation in the screening. If a patient confirms through this initial screening that she is out-of-adherence for one or more types of cancer screening (breast, cervical, and/or colorectal), the patient will be administered the Patient Health Questionnaire (PHQ)-9 to determine whether she meets criteria for depression. Those patients who score greater than or equal to 8 on the PHQ-9, do not have a terminal illness, are not pregnant, are not prisoners, are not decisionally impaired and are not active substance users will be asked to provide written informed consent to participate in the study. Patients will be told that study involvement entails speaking with a care manager at least once per month by phone or in-person, as they prefer, and they will be told about the two arms of the study and the randomization process. They will also be informed that participation will involve completing a baseline interview at the time of screening or within the week, as well as two follow-up interviews at 6 and 12-months after the baseline assessment.

The interviews can also take place by phone. Interview content will include basic demographics, questions about barriers to and use of medical and mental health services, physical and mental functioning including depression and anxiety symptoms, self-efficacy, stigma, attitudes towards cancer screening, satisfaction with care and decision-making, and health history information. Interviews will last approximately 45 minutes, and respondents will be compensated for their time: \$5 for the prescreening; \$10 for the first assessment; \$10 for the 6-month assessment; and \$15 for the 12-month assessment. This study is open to accrual of women only, because women are significantly more likely to suffer from depression, which has been shown to be related to cancer screening. We are also limiting our sample to women ages 50-64, since only women within this age range need all three types of preventive cancer screening: breast, cervical, and colorectal. Based on the demographics of patients treated at the health centers in our study, we expect that our female study sample will closely mirror the population of the Bronx. Subjects will not be excluded from participating in this study on the basis of race, ethnicity, socioeconomic status, or insurance status. Every attempt will be made to enter all eligible subjects into this protocol and therefore address the study objectives in a population representative of depressed females 50-64 years of age in the Bronx.

Finally, our analysis plan includes strategies to examine whether study outcomes differ by patients' demographic characteristics, including race, ethnicity, and language spoken. Patient recruitment and follow up need to be optimized in a randomized controlled trial. In order to maximize our likelihood of reaching our recruitment and follow-up goals, we have recruited and engaged three Community Health Centers and three NYC Health + Hospitals Corporation (HHC) practices that have worked with CDN and Einstein previously on NIH-funded research studies, and have the infrastructure and senior clinical leadership support for initiatives of this kind. Morris Height Health Center, Urban Health Plan, Montefiore CFCC, Segundo Ruiz Belvis D&TC, Morrisania D&TC and Lincoln Ambulatory Practice have all collaborated with CDN on previous NIH-funded randomized controlled trials with interventions and evaluations that include many of the same elements that are proposed in this study, and these practices have been successful at meeting their recruitment goals, and have achieved retention rates of 80% or greater.

For recruitment of patients, we will use a dual approach, clinician referral and identification of prospective participants by encounter data, which has been proven to be successful in previous CDN practice based research initiatives. In order to maximize the number of patients that complete the 6-month and 12-month study visits, we will use a standardized system to track participants through the study. We will obtain extensive locator information subsequent to informed consent, including addresses/phone and cell numbers of participants' family and friends as well caseworkers and social service agencies with which they are involved. Locator information will be updated at each study visit. An EXCEL database will be maintained to track projected study visit dates of each participant. Tangible incentives, including incentives in escalating amounts were built in for compensation of all study visits.

The proposed study will be open to women of all ethnic and racial backgrounds between the ages of 50 and 64 years who speak either English or Spanish. Based on data obtained from our previous cancer prevention projects in Bronx sites; we expect that this female sample will be half African-American and half Latino, roughly reflecting the racial and ethnic profile of the Bronx. We also expect that about half the sample will speak Spanish as their primary language.

I. CONFIDENTIALITY OF STUDY DATA

Confidentiality of each participant's self-report information from the interviews as well as information extracted from the medical records will be secured to ensure patient confidentiality. Study data that will record participant names include informed consents and contact forms. This information will be maintained by CDN staff and stored in a locked cabinet and separate from all other study data. All data sheets will be coded with an ID number to protect confidentiality and will be kept in locked filing cabinets that will be accessible only to the research staff. A master list with matching participant names and code numbers will be maintained in a password protected file on CDN's Local Area Network on separate sheets of paper, which will be kept in locked storage accessible only to the CDN staff. Any computers that are used to maintain project data will require passwords for access, and any files containing patient names will also be encrypted and protected by password. Participants will be told that discussions and interview data will be kept confidential. The CDN staff will never link participant responses with identifiable data – that will only be used for the purposes of recruiting participants.

The master list of names will be destroyed at the end of the project . The signed consent form will be kept in a locked file cabinet and then destroyed, along with all remaining project records, seven (7) years after the end of the project

All backup devices containing project data will be kept in a locked cabinet and only project staff authorized by the PI will have access to these data. Scientific presentations and publications will not use identifying information and will preserve the confidentiality of the participating CHCs, clinicians and patients; data will only be reported in aggregate form.

All investigators who have not done so already will complete necessary coursework regarding protection of human subjects and will receive certification from the Collaborative IRB Training Initiative (CITI). The CDN IRB and the IRBs of the three health centers will oversee this study. Also, a Data and Safety Monitoring Plan (DSMP) will be developed and will examine mental health adverse effects (e.g., frequency of severe depression requiring hospitalization, expressions of suicidality), as well as evidence of early superiority of either arm at increasing cancer screening, both requiring early study termination.

